
Table 1: Domains to be covered in AGYW pre- and post-intervention surveys.

Pre-Intervention Survey Domains	Post-Intervention Survey Domains

Demographics	Demographics
Clinic service uptake/use	Clinic service uptake/use ^(32, 130)
SRHR knowledge	SRHR knowledge ^(123, 131)
Violence and safety	Violence and safety ^(124, 125)
Gender norms	Gender norms ^(48, 132)
Agency	Agency ^(66, 133)
Mental health	Mental health ⁽¹²⁶⁾
	Intervention acceptability ⁽¹²⁹⁾
	Satisfaction with intervention/services ⁽¹²⁸⁾
	Feasibility ⁽¹²⁸⁾

Intervention Power Calculation and Sample Size Considerations: Power calculations and sample size for the adolescent health club component are determined based on the SRH knowledge measure.⁽¹²³⁾ With 85% power, in a two-arm comparison design (similar to round one in Figure 2 above), and based on data from a previous intervention study⁽¹³¹⁾ in which the investigators found a pre/post intervention difference of 1.3 and a standard deviation of 3, we will need 50 pairs or 100 participants in the adolescent clubs total. Broken into four groups, I plan for each group to be 25 participants. As this calculation does not take into consideration within-group analysis, it is a ≈20% overestimate, which allows for 20% loss to follow-up, or participant drop-out without loss of statistical power. However, to minimize bias, I am targeting 95% follow-up. 95% follow-up is based on our team's procedures for tracking and retaining adolescent health club participants. Specifically, we will make clear the participation expectations upon recruitment, consent, and the initial health club meeting. We will follow-up with participants who miss club sessions via cell phone and home visits as needed. These methods have been used by the research team in previous studies in the study area.

Implementation and Intervention Data Analysis

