For the adolescent health club component, the pilot study employs a waitlisted control group design. In this modified version of the stepped wedge design, all groups receive the intervention, and participants serve as their own controls. This design utilizes a smaller sample size of AGYW and fewer facilitators, making it more feasible for a K award, while still enabling all participants to participate in the intervention. The waitlisted control design also avoids some of the challenges associated with carryover effect that can occur in other crossover designs, as participants move unidirectionally from control to intervention. The adolescent health club curriculum (which takes approximately 2.5 months to complete) will be sequentially administered to four groups, each with a waitlisted control group. Individuals can be compared to themselves, and the other groups. Sequentially administering the intervention will be more feasible than administering the intervention simultaneously to separate neighborhood clusters, limiting the number of facilitators needed. Power calculations and sample size for the adolescent health club component are determined based on the SRHR knowledge measure. With 85% power, in a two-arm comparison design, and based on data from a previous intervention study in which the investigators found a pre/post intervention difference of 1.3 and a standard deviation of 3, we will need 50 pairs or 100 participants in the adolescent clubs total. Broken into four groups, this means that we will plan for each group to be 25 participants. As this calculation does not take into consideration within-group analysis, it is a slight overestimate, which allows for some attrition.

SECTION II: RESEARCH INVOLVING DRUGS, BIOLOGICS, RADIOTRACERS, PLACEBOS AND

If this section (or one of its parts, A or B) is not applicable, check off N/A and delete the rest of the section.

A. RADIOTRACERS

N/A

1. Name of the radiotracer: *Write here*

2. Is the radiotracer FDA approved? YES NO

If NO, an FDA issued IND is required for the investigational use unless RDRC assumes oversight.

3. Check one: IND# *Write here* or RDRC oversight (RDRC approval will be required prior to use)

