For the provider/staff sensitization component, a total of N=60 providers and staff will be recruited from the public and private clinics where AGYW were recruited for the formative quantitative survey. There will be two separate groups of 20 people each who undergo the sensitization workshop. The workshop will take place over four days. In previous work in the study area, retaining providers for a short intervention such as the one described in this proposal has not been a challenge and therefore we anticipate no challenges in recruiting the required sample size.

For the adolescent health club component, households with AGYW between the ages of 15 and 25 will be identified by Apnalaya's field team from randomly selected block sectors of the study area. AGYW and their mothers (if unmarried and under the age of 18) will be approached by a member of the research team and the adolescent health club intervention will be explained. If consent is obtained, the AGYW will be enrolled to either participate in the health club immediately or join the wait-list. An initial sample of 50 AGYW will be recruited (one group of 25 to begin intervention immediately, and one wait-list group). After the first intervention group has completed the health club curriculum, the wait-listed group will begin the intervention, and another 25 AGYW will be recruited for a wait-list. This will continue until four groups of 20-25 AGYW complete the health club intervention. Factoring in an attrition rate of 20%, the expected N at endpoint is 80. AGYW will complete the pre-intervention evaluation instrument upon enrollment. When young women complete the health club curriculum, they will also complete the post-intervention evaluation instrument. A sub-sample of young women will be asked

to participate in a focus group discussion to reflect on the club's impact and acceptability. To limit differences in

the time needed to assemble the health club groups, we will avoid recruiting during busy religious festivals/holidays (such as Ramadan) or vacation periods.

b. Describe how potential subjects are contacted.

Key informants and healthcare providers/staff for all phases will be contacted in the following ways: through in-person meetings, and snowball referrals/introductions via email (email recruitment template is attached) or cell phone.

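### The claim that 20% drop-out costs no power is unsupported, and false on the plan's own count of 50 pairs

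*Combined protocol and SAP*

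**What the plan says.** The Research Plan (Section I, item 4), under Intervention Power Calculation and Sample Size Considerations, sizes the health clubs on the SRH knowledge score: "With 85% power, in a two-arm comparison design", using "a pre/post intervention difference of 1.3 and a standard deviation of 3" from a previous study, "we will need 50 pairs or 100 participants in the adolescent clubs total". The groups follow from that: "Broken into four groups, I plan for each group to be 25 participants". The section then says the figure is too high by about 20%, because within-group analysis was left out, and that this "allows for 20% loss to follow-up, or participant drop-out without loss of statistical power". The next sentence sets a target of 95% follow-up in order to limit bias.

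Item 13, Statistical Considerations, repeats the calculation but says only that "it is a slight overestimate, which allows for some attrition". Section III, item 3a, Recruitment Procedures, makes 20% the planning assumption: "Factoring in an attrition rate of 20%, the expected N at endpoint is 80".

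No section gives alpha, the sidedness of the test, the pre/post correlation or a calculation behind the 20%. None says whether SD 3 belongs to the score or to the change in score.

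**The concern.** A calculation can absorb a 20% loss only if it starts with a 20% surplus. A figure of 50 pairs looks like the bare requirement of a paired test at 85%, with nothing added. The surplus is credited to within-group analysis, yet a paired test is already a within-group analysis, so the same gain may have been counted twice. If the calculation really was a comparison of two arms, 100 women look too few even before drop-out.

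At stake is an assurance to funders and ethics boards that the drop-out rate the protocol itself expects leaves power intact. They cannot verify it from what is written.

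**Working it through.** **Inputs.** Difference 1.3, SD 3, power 85%, 50 pairs or 100 women (Research Plan, sample size section); endpoint N of 80 (Recruitment Procedures). Assumed: two-sided alpha 0.05. Standardised difference d = 1.3/3 = 0.433.

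**1. Reproducing the plan's figure.** Paired test, normal approximation: n = (1.960 + 1.036)²/0.433² = 47.8, so 48 pairs. With the t distribution (noncentral t, n − 1 degrees of freedom, noncentrality d√n), the smallest n reaching 85% is 50, with power 85.2%. This matches the plan exactly. An independent two-arm comparison needs 2 × (1.960 + 1.036)²/0.433² = 95.6, so 96 per arm (97 by t), which does not match 50 per arm.

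**2. Taking 20% off the pair count.** The plan equates 50 pairs with 100 women, so 80 women are 40 pairs.

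| Pairs | d√n | Power |
|---|---|---|
| 50 | 3.06 | 85.2% |
| 40 | 2.74 | 76.2% |

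Keeping 50 pairs after 20% loss would take 50/0.8 = 62.5, so 63 pairs.

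**3. The two-arm reading, SD 3 as score SD, unadjusted.** Noncentrality is d√(n/2), with 2n − 2 degrees of freedom.

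| Per arm | d√(n/2) | Power |
|---|---|---|
| 50 | 2.17 | 57.4% |
| 40 | 1.94 | 48.2% |

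**4. The two-arm reading with baseline adjustment.** The SD becomes 3√(1 − ρ²), where ρ is an assumed pre/post correlation (normal approximation).

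| ρ | 50 per arm | 40 per arm |
|---|---|---|
| 0.5 | 70.6% | 60.9% |
| 0.7 | 85.9% | 77.4% |
| 0.75 | 90.6% | 83.4% |
| 0.8 | 95.1% | 89.8% |

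For 85% at 40 per arm: √(1 − ρ²) = (1.3 × √20/3)/(1.960 + 1.036) = 1.938/2.996 = 0.647, so ρ is about 0.76. At ρ = 0.7 the adjustment is what brings 100 women up to 85%; it leaves no surplus to lose.

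**5. Each woman as her own pair, SD 3 as the SD of the change.** Eighty completers are 80 pairs: d√80 = 3.88, power 96.9%. On this reading 50 women would already give 85%, and 100 women would give 99%.

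**The case against.** The strongest reply is that the plan places the 20% gain outside its calculation, so showing that 50 pairs is a bare requirement does not refute it. The design has women serve as their own controls, and the analysis section gives every woman a pre and a post measure. Read that way, 80 completers have 97% power and the no-loss statement is true. A mixed model could also hold 85% if the correlation is high enough. This much stands: the statement cannot be called false on every reading.

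A one-sided 5% test is another possible rescue, since 40 pairs then give 85.3%. But 50 pairs would then give 91.6%, not the stated 85%, and the plan does not offer sidedness as its reason.

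A reader might infer three stronger points, none of which the documents support.

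- *That 76% is the trial's power after drop-out.* No planned analysis pairs two different women. The 76% shows only that the 50-pair calculation has no slack.
- *That the attrition figures contradict each other.* In the sample size section 95% is a target and 20% an allowance, and the text sets them against each other knowingly. Recruitment Procedures says "This will continue until four groups of 20-25 AGYW complete the health club intervention". That is 80 to 100 completers, a range that contains both 80 and 95. Reading 20 as a hard minimum for each group goes beyond the text, where the sentence describes the cycle of running one group while recruiting the next.
- *That a 20% overestimate means a need of 100/1.2 = 83, so that 80 falls short.* Taking 20% off 100 gives 80, and the plan's figure is approximate.

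**Conclusion.** The no-loss statement is unsupported, and false on the plan's own 50-pair, 100-participant count: 85.2% falls to 76.2%. On the two-arm comparison that the section names, with SD 3 as the score SD and no adjustment, about 57% falls to 48%. Neither calculation holds a spare 20%.

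Two routes keep 80 completers at or above 85%. One is the within-woman paired comparison, at 97%; then neither the conversion of 50 pairs to 100 women nor the 85% describes this trial. The other is a baseline-adjusted comparison with a correlation of about 0.76 or more, which the plan does not state.

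These results assume two-sided 5%. The 97% takes SD 3 as the SD of the change; if it is the score SD, the SD of the change is 3√(2(1 − ρ)), which equals 3 only at ρ = 0.5. The 40 per arm is simply 80 divided by two, whereas a single round compares groups of 25.

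Two smaller points remain, as missing detail. The 20% is a tolerated loss in one section, the expected loss in another and unquantified in a third. Nothing says whether women who leave are replaced.

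**What to change.** In the Research Plan's sample size section and in item 13:

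- Delete the overestimate argument, and delete the statement that 20% loss costs no power.
- State alpha and sidedness, whether SD 3 is the SD of the score or of the change, and which comparison the power refers to.
- Report power for that comparison at the expected endpoint of 80 women. On present inputs this is about 97% for the within-woman paired test (SD 3 as change SD), or about 48% for an unadjusted comparison at 40 per arm (SD 3 as score SD). A baseline-adjusted value can be given with its assumed correlation, for example about 61% at 0.5 and 77% at 0.7.
- Do not print 76% as the trial's power.

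Use one planning attrition figure in the sample size section, item 13 and Recruitment Procedures, and keep 95% as the retention target. Add a sentence in Recruitment Procedures on whether women who leave are replaced.

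The cost is wording. The stated power for the between-group comparison becomes less favourable, and no enrolment is added.

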Survey with AGYW on care-seeking patterns and perceptions of healthcare quality and quantitative analysis: A random sample of AGYW seeking care at a set of public (N=3) and private (N=3) healthcare facilities in the study area will be selected and asked to participate in a brief, 20-30 minute survey using validated measures^(32, 45, 110) to discuss their patterns of healthcare-seeking (where they go for different problems, and what influences those choices), and their perceptions and experiences with adolescent healthcare. For unmarried participants under the age of 18, consent will be obtained from both a parent and the young woman. My collaborators and I have experience working in the study area and obtaining consent from parents, and we do not anticipate challenges obtaining consent. I will survey 20-25 AGYW from each facility, with a total N=100-150. Survey data will be entered into R,⁽¹¹¹⁾ and bivariate and multivariate analyses will be conducted to understand factors associated with AGYW treatment-seeking that may need to be addressed in the health clubs. Analyses will also explore quality of care to identify elements that may need to be incorporated into the provider sensitization. This survey will allow me to apply skills gained in Training Aim 1.

ADAPT-ITT Adaptation, Administration, and Production Phases

Theater testing with key stakeholders for intervention adaptations: Theater testing meetings will be held in which intervention sessions are presented and, in some cases, acted out to the group. Special attention will be given to adaptations needed due to COVID. Audience members' responses and post-meeting critiques of the material will be recorded and analyzed (see below). During the meetings, we will ask for both general feedback, as well as whether adolescent health club sessions need to be conducted separately with different age groups or based on marital status (married adolescents, regardless of age could have different needs than unmarried

adolescents). Separate meetings (up to 10 meetings total) will be held with the following stakeholder groups to present the intervention modules and elicit feedback on revisions or adaptations: 1) AGYW; 2) community members/KIIs; and 3) healthcare providers, CHVs, and NGO staff. Due to COVID, we will ensure groups remain smaller (no more than 5-10 participants) to allow adequate distancing. Additional meetings may be conducted after modifications are made to ensure agreement.

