The participants for the formative qualitative research (both key informants and young women) will be recruited primarily from Apnalaya's (community-based organization partnering on this study) established networks in the community over their 45 year-long work in the study area. As needed, additional recruitment will be from established networks of community leaders, NGO directors and staff, religious leaders, community health workers, and female community mobilizers. These networks have been established through the PI's previous work in the study area. Based on our previous work, we anticipate that these sources will easily yield the numbers of key informants (N=35-50) and adolescent girls and young women (N=20-70) required for the qualitative data collection in the formative stage. Mothers of girls interviewed will be asked to also participate in separate key informant interviews and theater testing groups, facilitating recruitment of this group.

For the quantitative portion of the formative research, a random sample of adolescent girls and young women (AGYW; ages 15-25 years old) seeking care at a set of public (N=3) and private (N=3) healthcare facilities in the study area will be referred by their healthcare provider and/or Apnalaya's health projects and asked to participate in a brief survey using validated measures to discuss their patterns of healthcare-seeking (where they go for different problems, and what influences those choices), and their perceptions and experiences with adolescent healthcare. Twenty to twenty- five AGYW will be surveyed from each facility, with a total N=150. Based on recent estimates of service usage, clinics in the study area see approximately 80-100 young women in the age range of 15-25 years old per month. Thus, we do not anticipate any challenges recruiting the sample size required for this quantitative survey.

Theater-testing group participants will be recruited similarly to the qualitative interviews above, and participants from the surveys may also be invited to join the theater-testing groups.

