AGYW for the qualitative data collection will be contacted primarily through Apnalaya's outreach activities, and through snowball referrals/introductions either in person or through cell phone. For the quantitative portion of the formative research, a random sample of adolescent girls and young women (AGYW; ages 15-25 years old) seeking care at a set of public (N=3) and private (N=3) healthcare facilities in the study area will be referred by their healthcare provider/Apnalaya health promotion team member to me or my research assistant and asked to participate in a brief survey.

For the adolescent health club component, households with AGYW between the ages of 15 and 25 will be identified by Apnalaya's field team from randomly selected block sectors of the study area. AGYW and their mothers (if unmarried and under the age of 18) will be approached by a member of the research team and the adolescent health club intervention will be explained. If consent is obtained, the AGYW will be enrolled to either participate in the health club immediately or join the wait-list.

c. Who is recruiting potential subjects?

Subjects will be recruited by the 3-4 members of Apnalaya's adolescent outreach team.

4. Assessment of Current Health Provider Relationship for HIPAA Consideration:

Does the Investigator or any member of the research team have a direct existing clinical relationship with any potential subject?

Yes, all subjects

Yes, some of the subjects

No

If yes, describe the nature of this relationship.

None of the members of the research team will have a direct existing clinical relationship with any potential subjects, however, healthcare providers and Apnalaya staff may tell potential subjects about the study, and refer them to me or my research assistant.

5. Request for waiver of HIPAA authorization: (When requesting a waiver of HIPAA Authorization for either the entire study, or for recruitment purposes only. Note: if you are collecting PHI as part of a phone or email screen, you must request a HIPAA waiver for recruitment purposes.)

Choose one:

For entire study

For recruitment/screening purposes only

For inclusion of non-English speaking subject if short form is being used and there is no translated HIPAA research authorization form available on the University's HIPAA website at hipaa.yale.edu.

i. Describe why it would be impracticable to obtain the subject's authorization for use/disclosure of this data: *Write here*

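### The formative care-quality survey is called a random sample, but the only route into it that the protocol describes is referral by the woman's provider or the partner NGO

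*Combined protocol and SAP*

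**What the plan says.** Section I, item 4 (Research Plan), in the paragraph on the survey of adolescent girls and young women (AGYW), states: "A random sample of AGYW seeking care at a set of public (N=3) and private (N=3) healthcare facilities in the study area will be selected". The survey covers care-seeking and perceived quality of care. The quality analyses are to identify content for the provider sensitization.

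Section III, item 3a, which answers how potential subjects are identified, keeps the label ("a random sample of adolescent girls and young women (AGYW; ages 15-25 years old) seeking care at a set of public" and private facilities) but says that these women "will be referred by their healthcare provider" and/or by the partner NGO's health projects, and are then invited to the survey. Item 3b, on how subjects are contacted, repeats the label and says that they "will be referred by their healthcare provider/Apnalaya health promotion team member to me or my research assistant and asked to participate in a brief survey". Item 3c says of the study as a whole: "Subjects will be recruited by the 3-4 members of Apnalaya's adolescent outreach team". Item 4 of the same section adds that "healthcare providers and Apnalaya staff may tell potential subjects about the study, and refer them to me or my research assistant".

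Item 3a also draws the 60 providers and staff for sensitization from the clinics used for this survey. It puts attendance at about 80 to 100 women aged 15 to 25 per month, without saying whether that is per clinic or for the whole area.

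**The concern.** A random sample needs a list or flow of eligible women and a selection rule that does not depend on what they think of their care. Referral supplies neither. A field team following the recruitment text would obtain the women whom a provider or NGO worker chose to send.

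Two different problems follow. On the provider route, the person whose care is rated can influence who rates it. This need not be deliberate: the background (A.2) reports that providers under the national programme concentrated on married and pregnant adolescents, so referral could under-represent unmarried women, whom the intervention also targets. On the NGO route the referrer is not one of the facilities named for rating. The issue there is that women in the NGO's network may differ from other attendees.

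What is at stake is the set of quality findings that guides the content of provider training, and any statement that those findings describe attendees in general.

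**Working it through.** **1. The plan's own figure.** Six facilities at 20 to 25 women give 6 × 20 = 120 to 6 × 25 = 150. The total of 150 in Section III (items 1 and 3a) is reproduced at 25 per facility. The lower bound of 100 in Section I (items 4 and 6) is not reached by 20 to 25 per facility. No precision calculation is given for this survey.

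**2. What a random sample needs, against what is written.**
- Frame (visit list, register or attendance on set days): none stated.
- Random draw or every-kth rule: none stated.
- Rule to refer every eligible attendee: none stated.
- Log of eligible women not referred: none stated.
- Route by which women are identified: referral by provider and/or NGO.

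By contrast, for the health clubs the protocol names a unit chosen at random, the block sector.

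**3. Room for discretion.** This depends on how the 80 to 100 per month is read.
- If per clinic: 20/100 = 20% to 25/80 = 31% of one month's eligible attendees are needed, so a referrer would pass on between about one in five and one in three.
- If the area total: 120/100 = 1.2 to 150/80 = 1.9 months of all attendees are needed, which leaves little room to choose unless recruitment is spread over a longer period.

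**4. Illustration of size.** The documents give no satisfaction or referral rates, so the inputs are assumptions. Let p be the true dissatisfied share and r the likelihood that a dissatisfied woman is referred, relative to a satisfied one. The share seen in the survey is p·r / (p·r + 1 − p). With p = 0.40 and every referral selective:
- r = 0.5: 0.20 / (0.20 + 0.60) = 25.0%, a shift of 15 points.
- r = 0.7: 0.28 / (0.28 + 0.60) = 31.8%, a shift of 8.2 points.

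If only half the sample came by selective referral:
- r = 0.5: 0.5 × 25.0% + 0.5 × 40% = 32.5%, a shift of 7.5 points.
- r = 0.7: 0.5 × 31.8% + 0.5 × 40% = 35.9%, a shift of 4.1 points.

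For scale, the 95% half-width at n = 150 and p = 0.40, ignoring clustering by facility, is 1.96 × √(0.40 × 0.60 / 150) = 7.8 points. Under these inputs the shift exceeds sampling error when all referrals are selective and falls below it when half are.

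**The case against.** The strongest reply is grammatical. The Research Plan says that the random sample is selected and then asked to take part, and in items 3a and 3b the thing referred is the random sample. A draw could come first, with the provider only making the introduction to the research assistant. That reading is possible. A reader might therefore infer that the claim of randomness is false, or that providers choose the sample; the text does not establish either. What stands is narrower: item 3a answers how subjects are identified, referral is the only mechanism it gives, and no prior draw is described anywhere.

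A second reply is that the provider share of referrals is unknown and may be small, since item 3c has the NGO's outreach team do the recruiting. This also stands, and it confines the conflict between rater and rated to referrals made by providers.

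A third is that the survey is there to find topics for training, not to estimate a prevalence. Even at 25% there would be about 38 dissatisfied respondents among 150 (0.25 × 150 = 37.5), and about 48 at 31.8%. The plan also has 20 to 70 in-depth interviews with AGYW, key informant interviews, theater testing and a community advisory board. So a reader might infer that selective referral would conceal the problems that the training should address, but the documents do not support that. It may weaken or distort the picture. The other sources reduce the dependence on this survey but do not make its sample random.

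**Conclusion.** The concern holds in a limited form. The survey is labelled random in three places, and the protocol gives no procedure that would make it so; following the written route yields a referred sample. Provider referral may bias quality findings that are used to shape training in the same clinics. NGO referral raises the separate question of whom the NGO reaches.

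The direction and size of any bias cannot be determined from the documents. The 25% to 32% range against a true 40% rests on assumed dissatisfaction and referral rates, and on every referral being selective. The one-in-five to one-in-three range rests on reading the monthly attendance as per clinic.

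A reader might extend the point to the trial's main comparison. That would be wrong: this is Aim 1 formative work, and neither the health-club comparison nor its sample size of 100 uses these data. The point is minor, but it is cheap to settle.

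**What to change.** Have the research assistant already in the plan select eligible AGYW from attendance on set survey days, either consecutively or every kth, and log those eligible, approached and refusing. Limit the provider's role to telling all eligible AGYW that the survey exists. State this in Section I item 4 and Section III items 3a and 3b.

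Set k from each facility's actual volume. If 80 to 100 per month is per clinic, k is about 4 (80/20 or 100/25) for one month of recruitment. If it is the area total, each facility sees about 13 to 17 per month (80/6 to 100/6) and k should be near 1. Every fourth woman would then take about 5 to 8 months to reach 20 to 25 (20 ÷ (16.7/4) = 4.8; 25 ÷ (13.3/4) = 7.5). The protocol should say which reading of the attendance figure is meant.

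The cost is scheduling the research assistant at six facilities and a modest change in field procedure, while keeping the private room and the parental consent that the plan requires for unmarried minors.

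If that is not workable, or the survey has already been done by referral, delete the word random in all three places, report a referred convenience sample, and do not generalise its quality estimates to all attendees. That costs only wording. If a prior random draw was in fact intended, describing its frame and selection rule would settle the point.
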